5.0 Stratification Factors: None**6.0 Registration Procedures**

6.1 Safety Analysis Phase

Prior to discussing protocol entry with the patient, call the ACCRU Registration Office [REDACTED] for dose level and to ensure that a place on the protocol is open for the patient.

6.11 Registration Procedures

To register a patient, fax [REDACTED] a completed eligibility checklist to the Academic and Community Cancer Research United (ACCRU) Registration Office between 8 a.m. and 4:30 p.m. central time Monday through Friday.

6.2 Phase II Cohort

6.21 To register a patient, access the ACCRU web page at [REDACTED] go to the Application section and click on “Registration” and enter the [REDACTED] registration/randomization application. The registration/randomization application is available 24 hours a day, 7 days a week. Back up and/or system support contact information is available on the Web site. If unable to access the Web site, call the Academic and Community Cancer Research United (ACCRU) Registration Office at [REDACTED]
[REDACTED]

The instructions for the registration/randomization application are available on the above web page under the Study Resources section, “Application Training.”

Prior to initiation of protocol study intervention, this process must be completed in its entirety and a ACCRU subject ID number must be available as noted in the instructions. It is the responsibility of the individual and institution registering the patient to confirm the process has been successfully completed prior to release of the study agent. Patient registration via the registration/randomization application can be confirmed in any of the following ways:

- Contact the ACCRU Registration Office [REDACTED]. If the patient was fully registered, the ACCRU Registration Office staff can access the information from the centralized database and confirm the registration.
- Refer to “Application Training” at [REDACTED] click on “Registration, Installation & Entry Instructions”.

6.3 Safety Analysis Cohort and Phase II Cohort

6.31 Correlative Research

A mandatory correlative research component is part of this study. The patient will be automatically registered onto this component (see Sections 3.0, 14.0 and 17.0).

6.32 Prior to accepting the registration, registration/randomization application will verify the following:

- IRB approval at the registering institution
- Patient eligibility
- Existence of a signed consent form
- Existence of a signed authorization for use and disclosure of protected health information

6.33 Documentation of IRB approval must be on file in the Registration Office before an investigator may register any patients. Approvals should be uploaded using the online ACCRU Regulatory Management System (ARMS).

In addition to submitting initial IRB approval documents, ongoing IRB approval documentation must be on file (no less than annually) with ACCRU. Approvals should be uploaded using online ACCRU Regulatory Management Systems (ARMS). If the necessary documentation is not submitted in advance of attempting patient registration, the registration will not be accepted and the patient may not be enrolled in the protocol until the situation is resolved.

Submission of annual IRB approvals is required until the study has been closed through your IRB.

- 6.34 At the time of registration, the following will be recorded:
- Patient has/has not given permission to store and use his/her sample(s) for future research to learn about, prevent, or treat cancer.
 - Patient has/has not given permission to store and use his/her sample(s) for future research to learn, prevent, or treat other health problems (for example: diabetes, Alzheimer's disease, or heart disease).
 - Patient has/has not given permission for ACCRU to give his/her sample(s) to outside researchers.
- 6.35 Treatment on this protocol must commence at an ACCRU institution under the supervision of a medical oncologist or hematologist.
- 6.36 Treatment cannot begin prior to registration and must begin ≤ 14 days after registration.
- 6.37 Pretreatment tests/procedures (see Section 4.0) must be completed within the guidelines specified on the test schedule.
- 6.38 All required baseline symptoms (see Section 10.54) must be documented and graded.
- 6.39a Study drug is available on site.
- 6.39b Blood draw kit is available on site. Kits must be used for this study.

7.0 Protocol Treatment

- 7.1 Safety Analysis Phase: Since this combination has not been studied to date, the first 6 patients treated at dose level 1 will be used as an early safety analysis per Section 16.4. If 2 or more patients experience a dose-limiting toxicity (DLT) as defined below, then the starting dose level will be adjusted and additional cohorts may be evaluated at dose levels -1 and -2 in the safety analysis phase as described in section 16.4. A conference call will

be held weekly amongst the investigators to discuss patients on study or proposed for accrual. Investigators are to contact the ACCRU Operations Office [contact] as soon as any DLT occurs.

7.11 Safety Analysis Dose Levels

Dose level	Brentuximab Vedotin	Nivolumab
-2	1.2 mg/kg IV Day 1	Omit
-1	1.8 mg/kg IV Day 1	Omit
*1	1.8 mg/kg IV Day 1	3 mg/kg IV Day 1

***starting dose level**

7.12 Definition of Dose Limiting Toxicity (DLT)

For this protocol, dose-limiting toxicity (DLT) will be defined as an adverse event occurring during the first cycle of treatment that is possibly, probably, or definitely related to study treatment and that meets one of the following:

- Any \geq Grade 4 non-hematological organ toxicity (except for Grade 4 nivolumab related diarrhea, pneumonitis, LFT elevations, that improve within 7 days)
- Any \geq Grade 4 hematological toxicity (excluding asymptomatic Grade 4 elevations in amylase or lipase)

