8.0 Dosage Modification Based on Adverse Events

Strictly follow the modifications in this table for the first **two** cycles, until individual treatment tolerance can be ascertained. Thereafter, these modifications should be regarded as guidelines to produce mild-to-moderate, but not debilitating, side effects. If multiple adverse events are seen, administer dose based on greatest reduction required for any single adverse event observed. Reductions or increases apply to treatment given in the preceding cycle and are based on adverse events observed since the prior dose.

ALERT: ADR reporting may be required for some adverse events (See Section 10)

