8.1 Dose Levels (Based on Adverse Events in Tables 8.2)

Brentuximab Vedotin	
	Starting Dose 1.8 mg/kg IV Day 1
1 st dose reduction	1.2 mg/kg IV Day 1
2 nd dose reduction	Discontinue

Nivolumab	
	Starting Dose 3.0 mg/kg IV Day 1
1 st dose reduction	Discontinue

Note: If either drug is discontinued, the patient may continue treatment with the other drug. If both drugs are discontinued, the patient will go to event monitoring per Section 18.0.

8.2 **Recommended Brentuximab Vedotin (BV) and Nivolumab Dose Modifications for Treatment-Associated Toxicity**

→ → Use the NCI Common Terminology Criteria for Adverse Events (CTCAE) version 4.0* unless otherwise specified ← ←			
CTCAE System/Organ/Class (SOC)	ADVERSE EVENT	AGENT	ACTION**
AT TIME OF RETREATMENT			
Investigations	Platelet count decreased	Brentuximab Vedotin (BV) and Nivolumab	Grade 3: Hold both BV and nivolumab until grade 2 or better, then reinstitute BV at 1.2 mg/kg and resume nivolumab at same dose.

→ → Use the NCI Common Terminology Criteria for Adverse Events (CTCAE) version 4.0* unless otherwise specified ← ←			
CTCAE System/Organ/Class (SOC)	ADVERSE EVENT	AGENT	ACTION**
Investigations	
Alanine aminotransferase Increased, Aspartate aminotransferase Increased, and/or Blood bilirubin increased
 
NOTE: increased bilirubin does not factor into dose modifications if secondary to Gilbert's syndrome.
	Brentuximab Vedotin (BV) and Nivolumab	
Grade 2 (>3 to 5 x ULN) AST or ALT elevations: Omit dosing for nivolumab; continue BV at the same dose level. Nivolumab may be resumed if the value improves to Grade 1 (≤ 3 x ULN) or better.
 
Grade 2 Bilirubin elevations (>1.5 to 3 x ULN): Omit dosing for nivolumab; continue BV at the same dose level. Nivolumab may be resumed if the bilirubin improves to Grade 1 (>ULN to 1.5 x ULN) or better.
 
Grade 2 (>3 to 5 x ULN) AST or ALT elevations WITH Grade 2 Bilirubin elevations (>1.5 to 3 x ULN): Hold both nivolumab and BV until ALT/AST value improves to Grade 1 (≤ 3 x ULN) or better and bilirubin value improves to Grade 1 (>ULN to 1.5 x ULN) or better.
 
Grade 3 (AST or ALT, OR Bilirubin elevations): Discontinue nivolumab; hold dosing for BV until toxicity is \leq Grade 2 or has returned to baseline, then resume at the same dose level.
 
Grade 4 (AST or ALT, OR Bilirubin elevations): Discontinue both nivolumab and BV. Patient should go to event monitoring, per Section 18.

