Immune System Disorders	Immune system disorders-other	Nivolumab	
If patient experiences immune-mediated rash Grade 3: Omit nivolumab dose until symptoms resolve and management with corticosteroids is complete, and then restart at the same dose level. If reoccurrence, discontinue nivolumab (continue brentuximab vedotin per protocol).
 
Grade 4: Permanently discontinue nivolumab (continue BV per protocol).
 
For any suspected immune-mediated adverse reactions, exclude other causes. Based on the severity of the adverse reaction, omit nivolumab, administer high-dose corticosteroids, and if appropriate, initiate hormone-replacement therapy. Upon improvement to Grade 1 or less, initiate corticosteroid taper and continue to taper over at least 1 month. Consider restarting nivolumab after completion of corticosteroid taper based on the severity of the event (continue BV per protocol).

Infections and Infestations	Encephalitis infection	Brentuximab Vedotin (BV) and Nivolumab	Discontinue Nivolumab if patient experiences immune-mediated encephalitis. Continue BV at same dose per protocol.

→ → Use the NCI Common Terminology Criteria for Adverse Events (CTCAE) version 4.0* unless otherwise specified ← ←			
CTCAE System/Organ/Class (SOC)	ADVERSE EVENT	AGENT	ACTION**
Nervous system disorders	Peripheral sensory neuropathy or peripheral motor neuropathy	Brentuximab Vedotin (BV)	
Grade 2 Reduce BV by 1 dose level and resume treatment; if already at 1.2 mg/kg, continue dosing at that level.
 
Grade 3 Omit BV until toxicity is ≤ Grade 2, then consult with PI
 
Grade 4 Discontinue BV. Continue Nivolumab at same dose per protocol.

Gastrointestinal disorders	Pancreatitis	Brentuximab Vedotin and Nivolumab	
Grade 2 Omit nivolumab until resolution, maximum 3 weeks. If > 3 weeks, discontinue nivolumab ONLY (continue BV per protocol).
 
Grade 3 or Grade 4, Discontinue BV . Hold nivolumab until grade 1 or better, then reintroduce. If it recurs, then discontinue nivolumab and patient should go to event monitoring, per Section 18.

Gastrointestinal disorders	Diarrhea	Brentuximab Vedotin (BV) and Nivolumab	
Grade ≥2: Hold both BV and nivolumab until resolution to baseline grade
 
Grade 3: Hold both BV and nivolumab and start corticosteroids until resolution to baseline grade.
 
Grade ≥4: Discontinue BV and Nivolumab. Patient should go to event monitoring, per Section 18.

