→ → Use the NCI Common Terminology Criteria for Adverse Events (CTCAE) version 4.0* unless otherwise specified ← ←			
CTCAE System/Organ/Class (SOC)	ADVERSE EVENT	AGENT	ACTION**
Gastrointestinal disorders	Colitis	Brentuximab Vedotin (BV) and Nivolumab	
Grade ≥2: Hold both BV and nivolumab until resolution to baseline grade
 
Grade 3: Hold both BV and nivolumab and start corticosteroids until resolution to baseline grade.
 
Grade ≥4: Discontinue BV and Nivolumab. Patient should go to event monitoring, per Section 18.

General disorders and administration site conditions	Fatigue	Brentuximab Vedotin (BV) and Nivolumab	Grade 3: Hold both BV and nivolumab until grade 2 or better
Endocrine Disorders	Adrenal insufficiency Hypothyroidism, Hyperthyroidism, Endocrine Disorders- Other (i.e. Hypophysitis, diabetes)	Nivolumab	Grade ≥3: Omit nivolumab until symptoms resolve and management with corticosteroids (if needed for symptoms of acute inflammation) is complete, and then restart at the same dose level. If reoccurrence, discontinue. (continue BV per protocol). Nivolumab should be continued in the presence of hormone replacement therapy, as long as no symptoms are present.
Respiratory, thoracic and mediastinal disorders	Pneumonitis	Brentuximab Vedotin (BV) and Nivolumab	
Grade ≥2: Hold both BV and nivolumab and start corticosteroids until resolution to baseline grade.
 
Grade ≥3: Discontinue BV and nivolumab and initiate treatment with high doses of corticosteroids. Patient should go to event monitoring, per Section 18.

→ → Use the NCI Common Terminology Criteria for Adverse Events (CTCAE) version 4.0* unless otherwise specified ← ←

CTCAE System/Organ/Class (SOC)	ADVERSE EVENT	AGENT	ACTION**
Respiratory, thoracic and mediastinal disorders	Cough	Brentuximab Vedotin (BV) and Nivolumab	Grade ≥2: Hold both BV and nivolumab and start corticosteroids until resolution to baseline grade. Grade ≥3: Discontinue BV and nivolumab and initiate treatment with high doses of corticosteroids. Patient should go to event monitoring, per Section 18.
Respiratory, thoracic and mediastinal disorders	Dyspnea	Brentuximab Vedotin (BV) and Nivolumab	Grade ≥3: Hold both BV and nivolumab up to four weeks until resolution to baseline grade. If no resolution patient should go to event monitoring, per Section 18.

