All other hematologic and non-hematologic	All other hematologic and non-hematologic	Brentuximab Vedotin (BV) and Nivolumab	Grade ≥ 2: Hold both BV and Nivolumab up to four weeks until resolution to Grade 1 or baseline. If no resolution patient should go to event monitoring, per Section 18.

* Located at http://ctep.cancer.gov/protocolDevelopment/electronic_applications/ctc.htm

** Use the following to describe actions in the Action column:

- Omit = The current dose(s) for the specified drug(s) during a cycle is skipped. The patient does not make up the omitted dose(s) at a later time.
- Hold/Delay = The current dose(s) of all drugs during a cycle is delayed. The patient does make up the delayed dose(s) when the patient meets the protocol criteria to restart drugs.
- Discontinue = The specified drug(s) are totally stopped.

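### Section 16.41 opens phase II on the DLT count alone, so some related cycle 1 toxicities that end both drugs carry no weight in that decision; a hold-and-review step in 16.4 would close the gap cheaply

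*Combined protocol and SAP*

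**What the plan says.** **The run-in rule.** Section 7.1 notes that the combination has not been studied before. Sections 7.1 and 16.4 use the first six patients at dose level 1 as an early safety analysis, with accrual halted meanwhile. Two or more DLTs lead to a lower dose level. With 0 or 1 DLT, Section 16.41 continues accrual into phase II at dose level 1.

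**What counts.** Section 7.12 limits DLTs to cycle 1 events that are at least possibly related. Non-hematologic events must be grade 4 or higher, and the definition carries the exception "except for Grade 4 nivolumab related diarrhea, pneumonitis, LFT elevations, that improve within 7 days".

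**What ends treatment.** Section 8.0 begins "Strictly follow the modifications in this table for the first" two cycles, and says that modifications "are based on adverse events observed since the prior dose". The Section 8.2 table then gives:
- Pneumonitis, and separately cough: "Grade ≥3: Discontinue BV and nivolumab and initiate treatment with high doses of corticosteroids".
- Diarrhea: "Grade ≥4: Discontinue BV and Nivolumab. Patient should go to event monitoring, per Section 18".
- Liver tests: "Grade 4 (AST or ALT, OR Bilirubin elevations): Discontinue both nivolumab and BV".

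The notes to the table say "Discontinue = The specified drug(s) are totally stopped". The table itself is headed "AT TIME OF RETREATMENT".

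**Who stays in the six.** Section 13.6 replaces a run-in patient who does not complete cycle 1 only when the reason is something other than toxicity.

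**The concern.** The run-in is the planned halt at which an untested combination is judged fit to open to further patients. Two groups of related cycle 1 events fall outside its count:

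- **Group (a):** grade 3 pneumonitis or cough. Section 8.2 ends both drugs for it.
- **Group (b):** nivolumab-related grade 4 diarrhea, pneumonitis or liver-test elevation that improves within 7 days. Section 8.2 probably ends both drugs here too.

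These patients are not replaced, so they stay among the six as patients without a DLT. Two or more of six could lose the whole regimen after one dose, and 16.41 as written would still open phase II.

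Pneumonitis is a plausible event here. Section 1.4 names it as the most frequent drug-related serious event with single-agent nivolumab (4.8%) and the most frequent event leading to discontinuation (2.9%). Section 15.17 lists it for brentuximab vedotin as well.

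**Working it through.** **1. The sections set side by side.**

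| Related cycle 1 event | DLT (7.12)? | Section 8.2 action | Counts in 16.52? |
|---|---|---|---|
| Grade 3 pneumonitis or cough | No | Both drugs stopped | No (grade 4+ only) |
| Nivolumab-related grade 4 diarrhea, pneumonitis or liver tests, improving within 7 days | No | Both drugs probably stopped | Yes |
| The same grade 4 events, not improving within 7 days | Yes | Both drugs stopped | Yes |

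The word *probably* in the second row reflects two readings. Section 8.0 grades on events since the prior dose, and 8.2 has no 7-day recovery clause, so both point to stopping. The heading about retreatment allows a reader to grade on the day of the next dose, when the event has already improved. For grade 3 pneumonitis or cough, the discontinue line also starts high-dose steroids, which is an action at onset, so the stopping reading is firmer.

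**2. No figure to reproduce.** The plan gives no operating characteristics for the 2-of-6 rule. The phase II table in 16.24 does reproduce by exact binomial calculation: 0.097, 0.293, 0.593 and 0.853 for declaring success, against the stated 0.10, 0.29, 0.59 and 0.85. This point does not touch it.

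**3. Chance that uncounted stops alone reach two of six.** With stop rate s per patient in cycle 1:

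P(X ≥ 2) = 1 − (1−s)^6 − 6s(1−s)^5

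- s = 0.029 (Section 1.4; single-agent, all treatment, pneumonitis only): 1 − 0.8381 − 0.1502 = 0.012
- s = 0.05 (assumed): 1 − 0.7351 − 0.2321 = 0.033
- s = 0.10 (assumed): 1 − 0.5314 − 0.3543 = 0.114
- s = 0.20 (assumed): 1 − 0.2621 − 0.3932 = 0.345

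The 2.9% is not a cycle 1 rate. Spread evenly over an assumed 6 to 9 cycles (exposure in that study is not given), it is 0.3% to 0.5% per cycle, and P(X ≥ 2) is about 0.0002 to 0.0003.

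**4. Would 16.52 catch them?** Group (a) never counts there. Suppose instead that every stop were grade 4, with the rule checked after each patient: 5 or more in the first 15, then 30% of all patients treated.

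| s (assumed) | First bullet only | Both bullets, 56 patients |
|---|---|---|
| 0.05 | 0.0006 | 0.001 |
| 0.10 | 0.013 | 0.02 |
| 0.20 | 0.164 | 0.30 |

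**5. Cost of a review trigger.** With DLT rate d and stop rate s, taken as independent, q = 1 − (1−d)(1−s), and the chance of any hold is P(X ≥ 2) for Bin(6, q).

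| d | s | q | DLTs alone | DLT or stop |
|---|---|---|---|---|
| 0.01 | 0.029 | 0.0387 | 0.0015 | 0.020 |
| 0.01 | 0.05 | 0.0595 | 0.0015 | 0.045 |
| 0.07 | 0.029 | 0.0970 | 0.061 | 0.108 |
| 0.07 | 0.05 | 0.1165 | 0.061 | 0.148 |

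The 7% is grade 4 neutropenia in the brentuximab phase 2 studies (Section 1.225), so it is high for one cycle. Over the median 9 and 6 cycles in Section 1.224 it is 0.07/9 = 0.008 and 0.07/6 = 0.012, about 1% per cycle.

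**The case against.** **The thresholds serve different purposes.** A DLT rule sets the starting dose, while Section 8.2 manages individual patients, and nothing requires the two to match. This stands. A reader might infer that Section 7.12 is wrong or should be tightened. The documents do not support that: the grade 4 threshold and the 7-day exemption read as deliberate choices. A second trigger does, however, give these events some weight in the run-in, and the sponsor may decline it.

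**There are other safeguards.** Section 7.1 has weekly investigator calls that cover patients proposed for accrual. Section 10.41 requires 24-hour reports of serious grade 3 to 5 events. Sections 16.214 and 16.22 contain provisos about excessive toxicity, and 16.25 lets adverse events inform termination. Section 16.51 provides twice-yearly DSMB review, and 16.52 permits discretionary suspension. So a reader who infers that these stops would go unseen goes too far: two such patients among six would very likely be discussed. What remains is that each safeguard is discretionary or comes later, and none conditions 16.41.

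**Section 16.52 is broader than its first bullet.** This stands. It covers all patients at the chosen dose and has no 7-day exemption, so group (b) events in the run-in count there. Group (a) still does not.

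**The rates are speculative.** This also stands. The only documented rate gives 0.01 or much less.

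**Section 8.2 is loosely worded.** The retreatment heading covers the whole table, and hold and discontinue lines overlap by grade. Both drugs are given on day 1 only, so a stop takes effect at cycle 2, and any trigger must be worded accordingly. Section 9.6 points to management algorithms in Appendix V, which is not in the supplied text; it may clarify the actions.

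**Conclusion.** The point holds as a cheap improvement to a safety rule, with medium confidence. Group (a) carries it: related cycle 1 grade 3 pneumonitis or cough ends both drugs, is never a DLT and never enters the numeric rule in 16.52. Group (b) adds to it with less certainty, because the 8.2 action is ambiguous and 16.52 does count these events.

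The size depends on a cycle 1 rate that the documents do not give. The chance of two or more uncounted stops in six is about 0.01 or less at the single-agent rate, and 0.03, 0.11 and 0.34 at assumed rates of 5%, 10% and 20%. It is material only if the combination proves clearly more toxic than single-agent data suggest, which is the situation that a run-in exists to detect.

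A reader might infer that the efficacy design is compromised. It is not: alpha, power and the response denominator are unchanged.

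**What to change.** Leave the DLT definition and the de-escalation rule as they are, and add one paragraph to Section 16.4:

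- Beside the DLT count, tabulate the patients who do not receive cycle 2 because a related toxicity arising in cycle 1 requires permanent discontinuation of both drugs under Section 8.2.
- If two or more of six have a DLT or such a stop, and DLTs alone are fewer than two, keep accrual halted until the study chair and statistician document a decision on opening phase II at that dose, with the DSMB informed.
- Do not de-escalate automatically in that case. Levels -1 and -2 omit nivolumab (Section 7.11), so that would abandon the combination.

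It would help to state in Section 8.2 whether a grade 4 event that has improved by the next dose still requires discontinuation.

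No new data are needed: grade 3 and 4 events are already submitted whatever their attribution (10.552), and accrual is already halted while each cohort is evaluated (16.4). The downside is a possible short delay. With an assumed 5% stop rate, the chance of any hold rises from 0.06 to 0.15 at an assumed 7% DLT rate, or from 0.002 to 0.05 at 1%. With a 2.9% stop rate the added chance is about 0.02 (0.020 − 0.0015) to 0.05 (0.108 − 0.061).
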